## 2) Medical conditions

- a) Evidence of worsening liver disease or hepatic decompensation, in the opinion of the investigator or Medical Monitor, during the screening period.
- b) Medical history of gastroesophageal varices, except if esophagogastroduodenoscopy performed within 12 months prior to the screening period has shown  $\leq$  Grade 1 varices and without red wale signs, as assessed by the investigator.
- c) **Not applicable per Revised Global Protocol v02** - History of alcohol consumption  $\geq 21$  units/week (male participants) or  $\geq 14$  units/week (female participants) within the 2 years prior to the biopsy used to determine eligibility. One drink “unit” or one standard drink is equivalent to 12 ounces of beer, 4 ounces of wine, or 1 ounce of hard liquor. Note: Participants should limit alcohol during their participation in the study ([Section 6.4](#)).
- d) History of bariatric surgery or intestinal bypass surgery within the 5 years prior to informed consent or planned during the conduct of the study.
- e) History of hepatocellular carcinoma.
- f) Participants who have: 1) current malignancy or 2) a previous malignancy up to 5 years prior to screening are excluded except for those with a documented history of cured nonmetastatic squamous cell skin carcinoma, basal cell skin carcinoma, or cervical carcinoma in situ. Participants who have a liver biopsy that is suspicious for malignancy, and in whom the possibility of malignancy cannot be reasonably excluded following additional clinical, laboratory, or other diagnostic evaluations, are also excluded.
- g) History of bone disease, including osteoporosis and osteomalacia, Paget’s disease of bone, or a history of unexplained fractures or fractures after minimal trauma as assessed by the investigator.
- h) Any disease or condition which, in the opinion of the investigator, might compromise participant safety (eg, hematologic, cardiovascular, pulmonary, renal, gastrointestinal, hepatic, skeletal, central nervous system, or complement-mediated disease).
- i) Any acute or chronic cardiovascular condition (eg, ischemic heart disease, congestive heart failure) considered clinically significant by the investigator.
- j) Uncontrolled hypertension, as defined by systolic blood pressure  $> 160$  mmHg and/or diastolic blood pressure  $> 100$  mmHg at screening, unless discussed with Medical Monitor. Blood pressure may be rechecked as clinically indicated.

- k) Known immunocompromised status, including but not limited to, individuals who have undergone organ transplantation or who are positive for human immunodeficiency virus (HIV) or have acquired immunodeficiency syndrome-related illness, as reported by the participant and/or documentation. NOTE: Testing for HIV must be performed at sites where mandated locally (see [APPENDIX 8](#)).
- l) History, within the last 2 years, of alcohol or drug abuse (in the opinion of the investigator), significant mental illness, or physical dependence on any opioid as per clinical discretion of the investigator.
- m) **Not applicable per Revised Global Protocol v02** - History of illegal IV drug use within the 3 years prior to screening.
- n) History of major surgery within 3 months of screening; this includes but is not limited to surgery that involves a risk to the life of the participant, specifically, within the cranium, chest, abdomen, or pelvic cavity.
- o) **Not applicable per Revised Global Protocol v02** - History of weight gain/loss  $\geq 10\%$  of body weight in the 6 months prior to the eligibility liver biopsy.
- p) Inability to tolerate IV medication or other study procedures, eg, lack of venous access.
- q) Inability to safely undergo a liver biopsy, in the opinion of the investigator.
- r) **Not applicable per Protocol Amendment 03** - History of severe acute respiratory syndrome coronavirus 2 (SARS-CoV-2) infection (either suspected or confirmed) within 4 weeks prior to signing consent. Additionally, in the case of prior SARS-CoV-2 infection, symptoms must have completely resolved and, based on investigator assessment in consultation with the Sponsor's Medical Monitor, there are no sequelae that would place the participant at a higher risk when receiving investigational treatment.

NOTE: COVID reverse transcription - polymerase chain reaction (RT-PCR) viral testing may be required prior to Randomization based on specific country/local guidelines, and the results of this testing may impact study participation. Testing results should be discussed with the Medical Monitor to confirm eligibility.

- s) History of alcohol consumption  $\geq 21$  units/week (male participants) or  $\geq 14$  units/week (female participants) within the 2 years prior to the biopsy used to determine eligibility. One drink "unit" or one standard drink is equivalent to 12 ounces (360 mL) of beer, 4 ounces (120 mL) of wine, or 1 ounce (30 mL) of hard liquor. Note: Participants should limit alcohol during their participation in the study ([Section 6.4](#)).
- t) History of illegal IV drug use within the 2 years prior to screening.
- u) **Not applicable per Protocol Amendment 03** - History of weight gain/loss  $\geq 10\%$  of body weight in the 3 months prior to the eligibility liver biopsy and any significant weight changes ( $\pm 10\%$  of body weight) during screening.
- v) History of severe COVID-19 infection (either suspected or confirmed) within 4 weeks prior to signing consent or a previous mild or moderate COVID-19 infection within 10 days prior screening. Additionally, for any COVID-19 infection prior to enrollment, symptoms must have completely resolved and, based on investigator assessment in consultation with the Sponsor's Medical Monitor, there are no sequelae that would place the participant at a higher risk when receiving investigational treatment.

NOTE: COVID reverse transcription - polymerase chain reaction (RT-PCR) viral testing may be required prior to Randomization based on specific country/local guidelines, and the

results of this testing may impact study participation. Testing results should be discussed with the Medical Monitor to confirm eligibility.

w) Any significant weight changes ( $\pm 10\%$  of body weight) in the 3 months prior and during screening.

### 3) Prior and concomitant therapy

- a) Participants taking any OTC vitamin A-containing supplements or multivitamins, or vitamin A-containing medications after signing the ICF.
- b) Participants unable to comply with restrictions and prohibited treatments.
- c) **Not applicable per Revised Global Protocol v02** - Participants who have taken other investigational agents within 3 months prior to the liver biopsy used to confirm eligibility or within 12 weeks or 5 half-lives prior to the first dose of study treatment, whichever is longer.
- d) Prior exposure to BMS-986263.
- e) The participant has received recent treatment with alternative therapies, which, in the opinion of the investigator, could potentially confound clinical or laboratory assessments (eg, herbal supplements).
- f) Concomitant use of nintedanib is prohibited. Prior use of nintedanib is permitted but must be discontinued at least 3 days before the first dose of study treatment.
- g) **Not applicable per Protocol Amendment 03** - Participants who have received live attenuated vaccine or investigational SARS-CoV-2 vaccine within 3 months prior to the first dose of study treatment. Participants who have received a vaccine approved for Emergency Use Authorization by the United States (US) Food and Drug Administration (FDA) may be considered for inclusion, after discussion with the Medical Monitor.
- h) Participants who have taken other investigational agents except for investigational SARS-CoV-2 vaccine within 3 months prior to the liver biopsy used to confirm eligibility or within 12 weeks or 5 half-lives prior to the first dose of study treatment, whichever is longer.
- i) Participants taking any anticoagulants after signing the ICF.
- j) Participants who have received live attenuated vaccine or investigational SARS-CoV-2 vaccine within 3 months prior to the first dose of study treatment. Participants who have received a vaccine approved for Emergency Use Authorization by the United States (US) Food and Drug Administration (FDA) or other applicable country-specific regulatory agencies may be considered for inclusion.

### 4) Physical and laboratory test findings

- a) Evidence of organ dysfunction or any clinically significant deviation from normal in physical examination, vital signs, ECG, or clinical laboratory determinations beyond what is consistent with the target population.
- b) The participant's baseline laboratory test results include abnormal values considered to be clinically significant by the investigator.
- c) **Not applicable per Revised Global Protocol v02** - The participant's laboratory test results at screening include any of the following:
  - Albumin  $< 3.5$  g/dL

- INR > 1.4 (participants who have an INR > 1.4 and who are taking an anticoagulant known to prolong INR may be included after discussion with the Medical Monitor)
- ALT value  $\geq 5 \times$  the ULN
- AST value  $\geq 5 \times$  the ULN
- Total bilirubin > 1.5 mg/dL, unless participant has a diagnosis of Gilbert Syndrome and direct bilirubin  $\leq$  ULN
- Platelet count < 140,000/ $\mu$ L
- Hemoglobin A1c  $\geq 9.0\%$
- Serum vitamin A (retinol) > ULN

d) Glomerular filtration rate < 30 mL/min/1.73 m^2 according to the Modification of Diet in Renal Disease equation at screening.

e) Centrally-read DXA scan BMD T-Score of -2.5 or less at the femoral neck, total hip, or lumbar spine during screening (in participants 40 years of age or older).

f) **Not applicable per Protocol Amendment 03** - The participant's laboratory test results at screening include any of the following:

- Albumin < 2.8 g/dL
- INR > 2.2
- ALT value  $\geq 5 \times$  the ULN
- AST value  $\geq 5 \times$  the ULN
- Total bilirubin > 3.0 mg/dL, unless participant has a diagnosis of Gilbert Syndrome and direct bilirubin  $\leq$  ULN
- Platelet count < 85,000/ $\mu$ L
- Hemoglobin A1c  $\geq 9.0\%$
- Serum vitamin A (retinol) > ULN

g) The participant's laboratory test results at screening include any of the following:

- Albumin < 2.8 g/dL
- International normalized ratio (INR) > 2.2
- ALT value  $\geq 5 \times$  the ULN
- AST value  $\geq 5 \times$  the ULN
- Total bilirubin > 3.0 mg/dL, unless participant has a documented diagnosis of Gilbert Syndrome, provided that total bilirubin is < 4.0 mg/dL and direct bilirubin is  $\leq$  ULN
- Platelet count < 85,000/ $\mu$ L
- Hemoglobin A1c  $\geq 9.5\%$
- Serum vitamin A (retinol) > ULN

## 5) Allergies and adverse drug reaction

- a) Not applicable per Revised Global Protocol v01.
- b) History of allergies to soybeans or eggs.

c) History of allergy

## 6) Other exclusion criteria

- a) Prisoners or participants who are involuntarily incarcerated. (Note: Under certain specific circumstances and only in countries where local regulations permit, a person who has been imprisoned may be included or permitted to continue as a participant. Strict conditions apply and BMS approval is required.)
- b) Participants who are compulsorily detained for treatment of either a psychiatric or physical (eg, infectious disease) illness.
- c) Any factor, which in the opinion of the investigator would jeopardize the evaluation or safety or be associated with poor adherence to the protocol.

Eligibility criteria for this study have been carefully considered to ensure the safety of the study participants and that the results of the study can be used. It is imperative that participants fully meet all eligibility criteria.

A horizontal bar chart consisting of 15 black bars of varying lengths. The bars are arranged in a single row, with some having small white gaps between them. The lengths of the bars range from approximately 10% to 90% of the total width of the chart area. There is no explicit title or axis label provided for this chart.

## 6.4 Lifestyle Restrictions

Participants should not consume  $\geq 7$  units/week of alcohol during the study. One drink “unit” or 1 standard drink is equivalent to 12 ounces (360 mL) of beer, 4 ounces (120 mL) of wine, or 1 ounce (30 mL) of hard liquor.

During the study, OTC herbal supplements or multivitamins containing vitamin A (including Cod liver oil), or other medications that may contain vitamin A are prohibited ([Section 7.7.1](#)). Prior to starting study treatment and throughout the study, the investigator will educate participants about vitamin A-containing foods, medications, and herbal supplements

(<https://ods.od.nih.gov/factsheets/VitaminA-Consumer>, or equivalent country-specific national dietary recommendations), as well as the signs and symptoms of [REDACTED]. Consultation with a nutritionist should be considered if necessary.

## 6.5 Dietary and Lifestyle Counseling

At the screening visit, after receiving the signed ICF, sites will provide all participants with the following dietary and lifestyle counseling:

- Reduce body weight (if obese or overweight) through diet and exercise
- Follow a balanced diet
- Increase physical activity
- Avoid alcohol as much as possible

## 6.6 Screen Failures

Screen failures are defined as participants who consent to participate in the clinical study (ie, enroll) but are not subsequently randomized into the study. A minimal set of screen failure information is required to ensure transparent reporting of screen failure participants, to meet the Consolidated Standards of Reporting Trials publishing requirements, and to respond to queries from regulatory authorities. Minimal information includes date of consent, demography, screen failure details, eligibility criteria, and any serious AEs. [REDACTED]

### 6.6.1 Retesting During Screening Period

Participant Re-enrollment: This study permits the re-enrollment of a participant that has discontinued the study as a pretreatment failure (ie, participant has not been randomized/has not been treated). If re-enrolled, the participant must be re-consented.

Retesting of laboratory parameters and/or other assessments within any single screening or lead-in period will be permitted (in addition to any parameters that require a confirmatory value). The most current result prior to Randomization is the value by which study inclusion will be assessed, as it represents the participant's most current, clinical state. Laboratory parameters and/or assessments that are included in [Table 1](#), Screening Procedural Outline may be repeated in an effort to find all possible well-qualified participants. Consultation with the Medical Monitor may be needed to identify whether repeat testing of any particular parameter is clinically relevant.

Participants who are screen failures may be rescreened only once; additional rescreening may be allowed after consultation with the Medical Monitor. An additional rescreening is permitted for study participants who have failed screening due to SARS-CoV-2 infection. All participants who are re-enrolled will be assigned a new participant identification. For participants who are rescreened, [REDACTED] DXA scan assessments can be reused without repeating if performed 3 months prior to rescreening visit ([Section 2](#)).

## 7 TREATMENT

Study treatment is defined as any investigational treatment(s), marketed product(s), placebo, or medical device intended to be administered to a study participant according to the study randomization or treatment allocation.

Study treatment includes both investigational [medicinal] product (IP/IMP) and non-investigational [medicinal] product (nonIP/nonIMP) as shown in Table 5.

An IP, also known as IMP in some regions, is defined a pharmaceutical form of an active substance or placebo being tested or used as a reference in a clinical study, including products already with a marketing authorization but used or assembled (formulated or packaged) differently than the authorized form, or used for an unauthorized indication, or when used to gain further information about the authorized form.

Other medications used as support or escape medication for preventative, diagnostic, or therapeutic reasons, as components of the standard of care for a given diagnosis, may be considered as nonIP.

**Table 5:** Study Treatments

Product Description/Class and Dosage Form	Potency	IP/NonIP	Blinded or Open-Label	Packaging/Appearance	Storage Conditions (Per Label)
BMS-986263 for injection	10 mg per vial; 3 mg/mL after reconstitution	IP	Blinded a	[REDACTED]	[REDACTED]
Placebo b for BMS-986263 for injection/	NA	IP	Blinded a	[REDACTED]	[REDACTED]

IP = investigational product; IV = intravenous; NA = not applicable

a The medication is provided to the pharmacy open-label, and an unblinded pharmacist (or another appropriately delegated qualified individual) will prepare the blinded solutions for IV infusion.

b [REDACTED]

## 7.1 Treatments Administered

The investigator must ensure that the IP will be used only in accordance with the protocol and Pharmacy Manual. The selection and timing of dose for each participant is shown in Table 6.

**Table 6: Study Treatment Doses, Dosing Frequency, and Route of Administration**

Study Treatment	Unit Dose Strength(s)/Dosage Level(s)	Frequency of Administration	Route of Administration
45 mg BMS-986263		QW	IV infusion
90 mg BMS-986263		QW	IV infusion
Placebo		QW	IV infusion

IV = intravenous; QW = once every week

### Treatment Preparation

An unblinded pharmacist (or another appropriately delegated qualified individual) will prepare matching IV infusion solutions [REDACTED]

[REDACTED] according to the participant's treatment assignment ([Section 7.2](#)).  
[REDACTED]

Please refer to the Pharmacy Manual for complete information on BMS-986263 and placebo storage, handling, and exact volumes, and instructions on the preparation of study treatment infusion.

### Treatment Administration

The study treatment will be infused using an IV pump, as described in the Pharmacy Manual. The IV access will be kept open before and after the infusion with sufficient quantities of 0.9% saline or 5% dextrose in water to assure it remains patent. The time the infusion is initiated/adjusted/concluded, including any interruptions, will be documented in the electronic case report form (eCRF).

Study treatment infusions should be administered on the same day of each week to the extent that this is possible with a window of  $\pm$  3 days. Infusions must be separated by at least 3 days. At the study treatment infusion visits, all study procedures and assessments must be completed prior to initiation of the study treatment infusion (with the exception of PK samples collected during and postinfusion). When fasting is required for the preinfusion study procedures, participants may eat once all of the preinfusion testing and assessments are performed.

### **7.1.1      *Study Treatment Infusion Rate***

The study medication is suggested to be infused in a step-wise approach as described below, as used in the IM025006 final clinical study report (CSR). The total dose of the study medication should not be infused in less than 60 minutes. The initial rate of the administration should not be any greater than the initial rate specified below.

Recommended blinded treatment stepped titration infusion rates:

The infusion rates may be decreased by the investigator based on the participant's previous tolerance of the infusion, including any IRRs that may have occurred in the past. Consultation with the Medical Monitor is recommended if any other modification of these recommended infusion rates is being considered. In addition, the investigator may choose to pause the infusion depending on the participant's clinical condition and history. If clinical signs and/or symptoms indicate an IRR, the infusion may be interrupted. If the infusion is interrupted for any reason, the infusion may be restarted at the discretion of the investigator.

Additional details on IRRs, including the management of IRRs, are provided in [Section 9.2.9](#).

### **7.1.2      *Premedication***

Based on the discretion of the investigator, the participants may be administered IV or oral premedication approximately [REDACTED], respectively, before the start of the study treatment infusion. The investigator may choose to administer IV antihistamines (eg, diphenhydramine hydrochloride 50 mg, famotidine 20 mg) or oral antihistamines (eg, levocetirizine 5 mg) and/or IV corticosteroids (eg, hydrocortisone 100 mg or methylprednisolone sodium succinate 125 mg).

Participants who receive antihistamine premedication should be advised that the premedication may be sedating and cautioned against driving or operating heavy machinery for at least 3 hours after administration. For sites participating in the [REDACTED], the pretreatment [REDACTED] activities must be completed prior to the start of any premedication.

## **7.2            *Method of Treatment Assignment***

At the time of the screening visit, before any study-related procedures are performed, the investigative site will access the enrollment option of the IRT system for assignment of a subject number. This number is assigned sequentially by the system and will be unique across all sites. If a potential participant is rescreened, a new identification number will be used.

Before the study is initiated, each user (at investigative sites) will receive log-in information and directions on how to access the IRT. Study treatment will be dispensed and administered at the study visits as listed in SOA ([Section 2](#)).

Eligible participants will be centrally randomized using IRT to receive BMS-986263 or placebo according to a computer-generated block randomization scheme and in accordance with stratification criteria. Randomization to a treatment group will be assigned prior to dosing.

### **7.3      Blinding**

#### **7.3.1    *Maintaining the Blind***

Blinded treatment assignments will be managed using IRT. All infusion solutions (prepared by an unblinded pharmacist (or another appropriately delegated qualified individual) at the investigative site per the Pharmacy Manual) are matching in appearance, and will be supplied as shown in [Table 6](#). Investigative site staff, Sponsor and designee personnel, and participants and their families will remain blinded to treatment assignments.

The investigative site staff will include the following:

- An unblinded pharmacist (or another appropriately delegated qualified individual), who will be responsible for preparing the infusion solutions and providing in a blinded manner to the study team, ensuring that the infusion solutions are protected from light as described in the Pharmacy Manual. The unblinded pharmacist (or another appropriately delegated qualified individual) must not reveal potentially unblinding information to the study team.

#### **7.3.2    *Circumstances for Unblinding***

Blinding of treatment assignment is critical to the integrity of this clinical study. However, in the event of a medical emergency or pregnancy in an individual participant in which knowledge of the IP is critical to the participant's management, the blind for that participant may be broken by the investigator. The participant's safety takes priority over any other considerations in determining if a treatment assignment should be unblinded.

Before breaking the blind of an individual participant's treatment, the investigator should determine that the unblinded information is necessary (ie, that it will alter the participant's immediate medical management). In many cases, particularly when the emergency is clearly not related to the IP, the problem may be properly managed by assuming that the participant is receiving active product. It is highly desirable that the decision to unblind treatment assignment be discussed with the Medical Monitor, but the investigator always has ultimate authority for the decision to unblind. The actual TASK of unblinding can be delegated by the investigator to a designee assigned the task on the Delegation of Authority. The principal investigator or appointed designee should only call in for emergency unblinding AFTER the decision to unblind the participant has been documented.

In case of an emergency, the investigator has unrestricted access to randomization information via IRT and is capable of breaking the blind through the IRT system without prior approval from the Sponsor. After the unblinding, the investigator shall notify the Medical Monitor and/or Study Director. The method of unblinding for emergency purposes is described in the reference manual(s).

In cases of accidental unblinding, contact the Medical Monitor and ensure every attempt is made to preserve the blind. Any request to unblind a participant for nonemergency purposes should be discussed with the Medical Monitor.

Designated staff of BMS Research & Development may be unblinded (obtain the randomization codes) prior to database lock to facilitate the bioanalytical analysis of PK samples [REDACTED]. A bioanalytical scientist in the Bioanalytical Sciences department of BMS Research & Development (or a designee in the external central bioanalytical laboratory) will be unblinded to (may obtain) the randomized treatment assignments in order to minimize unnecessary bioanalytical analysis of samples.

[figure not shown]
The study will be unblinded once all participants have completed the Follow-up Week 4 visit and all data have been collected through that time point to facilitate analyses ([Section 10.4.4](#)).

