### **5.1.2 *Treatment Period and Follow-up***

Participants meeting eligibility criteria during the screening period will enter the treatment period. Approximately 270 participants will be randomized via interactive response technology (IRT) in a 1:1:1 ratio to receive 45 mg BMS-986263 QW, 90 mg BMS-986263 QW, or placebo QW by IV infusion in a double-blind manner.

Participants will be stratified at Randomization by the presence of definite steatohepatitis on biopsy (yes versus no). At least 80% of participants will be required to have definite steatohepatitis on the biopsy used to confirm eligibility. Participants will receive study treatment via IV infusion for a total of 12 weeks. Liver biopsy will be performed at Week 12.

After 12 weeks (Day 85) of treatment or after early treatment discontinuation, participants will enter the 24-week follow-up period, during which participants will not receive investigational treatment. After all participants complete the Follow-up Week 4 visit, the study will be unblinded and analyses of the available Week 12 data will be conducted ([Section 10.4.4](#)). Participants who discontinue study treatment before the Week 11 Visit will have an Early Treatment Termination (ETT) visit and will continue into the 24-week follow-up period.

See the SOA in [Table 2](#) and [Table 3](#) ([Section 2](#)).

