## **5.3 End of Study Definition**

The start of the study is defined as the first visit for first participant screened. End of study (EOS) is defined as the last visit or scheduled procedure shown in the SOA ([Section 2](#)) for the last participant. Study completion is defined as the final date on which data for the primary endpoint was or is expected to be collected, if this is not the same. The end of the study for analysis of [REDACTED] samples is included in [REDACTED].

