Tissue from biopsies performed during the study will be collected for analysis. Histological assessments related to efficacy of BMS-986263 will be performed by central pathology reading. The on-treatment liver biopsy results will remain blinded to site personnel until at least post-database lock. If local pathology assessment is necessary, a portion of the sample should be submitted to a local pathologist following the standard procedure utilized by the study site. Any local incidental findings of potential clinical relevance identified at this post-baseline assessment that are not directly associated with the objectives of the protocol should be evaluated and handled by the study investigator as per standard medical/clinical judgment.

Liver tissue should be collected using a 16-gauge (or larger lumen) cutting needle (eg, Bard, Microvasive, or TruCut) whenever possible. Use of suction needles (eg, Menghini, Jamshedi, or Klatskin) should be avoided because they may cause fragmentation of fibrotic specimens and impede the evaluation of fibrosis. Use of suction needles should be discussed with the Medical Monitor. At least 2 cm length of tissue should be obtained. Additional details on the acquisition, quality requirements, histological preparation, and shipping of histological samples are in the Laboratory Manual.

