#### **10.4.4 Week 12 Analyses**

After all participants have either completed the Follow-up Week 4 visit or have discontinued the study prior to the Follow-up Week 4 visit, the study will be unblinded and the primary analysis for the study will be conducted.

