#### **10.4.5 Interim Analysis**

Two interim analyses may be performed after approximately 30% and 50% of participants have either completed the Follow-up Week 4 visit or have discontinued the study prior to the Follow-up Week 4 visit.

The purpose of the 30% interim analyses will be to assess futility. The DMC will review the available data to make recommendation on the following options:

- Continue the study as planned
- Terminate the study for futility

The futility decision criteria and the review process by the DMC will be specified in the DMC Charter and the DMC SAP.

The purpose of the 50% interim analysis will be to help in early planning for accelerating further clinical development of the compound. No formal test of statistical significance is planned. Results will be descriptive and based on the estimation of effect size and associated CIs. Thus, no adjustments to overall Type I error will be made.

The interim analysis results on both occasions will be reviewed by the independent DMC; and the Sponsor's Internal Review Committee (IRC) if needed. The blinding to investigators and the study team will be maintained until the end of the study.

Within the DMC Charter, for each interim analysis, the Sponsor will specify:

- Conditions under which interim results could be shared with select individuals within BMS to help in early planning of clinical development of the compound
- Steps taken to ensure the blinding of the other BMS personnel (that are not unblinded) and investigators to interim results
- Statistical summaries that will be prepared for review

Details of the interim analyses will be described in the DMC SAP and DMC Charter, which will be revised and finalized prior to the DMC meeting.

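### The plan unblinds the study after Follow-up Week 4 without saying for whom, while Section 10.4.5 keeps investigators and the study team blinded to the end of the study

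*Combined protocol and SAP*

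**What the plan says.** Four places unblind the study as a whole.

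- Sections 1.1 and 5.1.2: "After all participants complete the Follow-up Week 4 visit, the study will be unblinded", followed by analysis of the Week 12 data.
- Section 7.3.2: "The study will be unblinded once all participants have completed the Follow-up Week 4 visit and all data have been collected through that time point". The sentence goes on to give analysis as the purpose and refers to Section 10.4.4.
- Section 10.4.4 sets the trigger as all participants having "either completed the Follow-up Week 4 visit or have discontinued the study prior to the Follow-up Week 4 visit, the study will be unblinded", followed by the primary analysis.

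Section 10.4.5, on the interim analyses, says: "The blinding to investigators and the study team will be maintained until the end of the study". Section 5.3 states that "End of study (EOS) is defined as the last visit or scheduled procedure shown in the SOA" for the last participant, and Table 3 labels the Follow-up Week 24 visit as EOS.

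Three other statements bear on the point. Section 7.3.1 says, with no end date: "Investigative site staff, Sponsor and designee personnel, and participants and their families will remain blinded to treatment assignments". Section 9.1.2 says: "The on-treatment liver biopsy results will remain blinded to site personnel until at least post-database lock". Section 7.3.2 also says: "Any request to unblind a participant for nonemergency purposes should be discussed with the Medical Monitor".

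**The concern.** One rule ends the blind at about the last Follow-up Week 4 visit, for unspecified recipients. The other keeps investigators and the study team blinded until the last Follow-up Week 24 visit. A site or study team member following the protocol cannot tell which applies between those dates.

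Data are still being collected then. Table 3 collects adverse events through the last visit, and Appendix 3 leaves causality to the investigator's judgement. Infusion-related reactions are confined by Section 9.2.9 to 24 hours from the start of an infusion. That leaves bone fracture as the main potential event of special interest (Section 9.2.8) still open during off-drug follow-up. Section 5.4 gives the period a purpose of its own, off-treatment durability through Follow-up Week 24. If sites or participants learned the assignment, event reporting, causality assessment and retention at Follow-up Weeks 12 and 24 could be affected.

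**Working it through.** **1. The two end points.** The Week 12 unblinding falls at or after the last Follow-up Week 4 visit (Sections 1.1, 5.1.2, 7.3.2, 10.4.4). The end of the study is the last participant's last scheduled visit or procedure (Section 5.3), at Follow-up Week 24 (Table 3). Section 5.3 defines study completion separately, by the primary endpoint data. Section 10.4.5 uses the other term, end of the study.

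**2. Timeline check.** Screening of up to 12 weeks, treatment of 12 and follow-up of 24 give 12 + 12 + 24 = 48 weeks, which reproduces the total duration in Section 1.2.

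**3. Gap for the last participant.** 24 − 4 = 20 weeks, or 140 days. With the Table 3 windows of ±3 days at Week 4 and ±7 days at Week 24:
- shortest: 140 − 3 − 7 = 130 days (18.6 weeks)
- longest: 140 + 3 + 7 = 150 days (21.4 weeks)

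Two scheduled visits, Follow-up Weeks 12 and 24, fall after the trigger.

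**4. Share of participants still in follow-up.** Accrual is not stated, so this step is illustrative. Let accrual last A weeks and let unblinding come L weeks after the last Follow-up Week 4 visit. Counting from randomisation, Follow-up Week 4 is week 12 + 4 = 16 and Follow-up Week 24 is week 12 + 24 = 36. A participant randomised at week t is still in follow-up if t + 36 > A + 16 + L, that is, t > A − (20 − L). Everyone is assumed to complete follow-up.

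- Uniform accrual: share = (20 − L)/A
- Accrual rate rising linearly from zero: share = 1 − (1 − (20 − L)/A)²
- Accrual rate falling linearly to zero: share = ((20 − L)/A)²

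L = 8 is an assumed allowance for the data-collection condition in Section 7.3.2.

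| Accrual pattern | L | A = 52 | A = 104 | A = 156 |
|---|---|---|---|---|
| Uniform | 0 | 20/52 = 38.5% | 20/104 = 19.2% | 20/156 = 12.8% |
| Uniform | 8 | 12/52 = 23.1% | 12/104 = 11.5% | 12/156 = 7.7% |
| Rising | 0 | 62.1% | 34.8% | 24.0% |
| Rising | 8 | 40.8% | 21.7% | 14.8% |
| Falling | 0 | 14.8% | 3.7% | 1.6% |
| Falling | 8 | 5.3% | 1.3% | 0.6% |

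Of 270 participants, the uniform rows are 104, 52 and 35 with no lag, and 62, 31 and 21 with the 8-week lag. These are examples, not bounds.

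**5. If Section 10.4.5 covers only the interim looks.** Then only Section 7.3.1 keeps sites and participants blinded after the Week 12 analysis. It is undated and names site staff, sponsor personnel and participants together. The analysis must end it for at least some sponsor personnel, and nothing in the sentence separates the sites from them. Section 9.1.2 covers biopsy results, not treatment codes, and does not say which database lock is meant. The rule on nonemergency requests in Section 7.3.2 has no end date. Sections 1.1 and 5.1 attach the term double-blind to the treatment period and describe follow-up only as off investigational treatment.

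**The case against.** The strongest reply is that the Section 10.4.5 sentence stands among text on the interim looks and the DMC Charter, so it may mean only that those looks do not break the blind. That reading is plausible and would remove the direct conflict. It would not supply a rule for the follow-up period, as step 5 shows.

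A second reply is that the plan plainly intends sites to stay blinded. Unblinding is tied to analysis, no passage releases codes to sites, and Section 7.3.2 gives certain sponsor and laboratory staff earlier access for PK work without unblinding sites. This stands as evidence of intent, but none of it says who remains blinded once the study is unblinded.

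Third, text has been removed near the Section 7.3.2 sentence and may name the recipients. If it does, what remains is to align that sentence with Sections 10.4.5 and 7.3.1.

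Fourth, the consequence is limited. The primary and other Week 12 biopsy endpoints are unaffected, and BMD is assessed by a central vendor (Section 9.4.5). That is correct. The shares in step 4 also rest on assumed accrual, and being in follow-up is not the same as being unblinded.

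**Conclusion.** The concern holds. As written, the four unblinding statements and Section 10.4.5 read with Section 5.3 cannot all be followed. On the narrower reading of Section 10.4.5, the plan still lacks a dated rule on who stays blinded in follow-up.

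The firm figure is the gap of about 20 weeks for the last participant, assuming that participant completes follow-up. How many participants it touches cannot be fixed from the documents. No alpha, power or sample size figure changes. Harm to the late safety data and to retention follows only if assignments reach sites or participants. The change should be made, with medium confidence because of the removed text and the possible interim-only reading.

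**What to change.** - In Sections 7.3.2 and 10.4.4, mirrored in 1.1 and 5.1.2, limit the Week 12 unblinding to the sponsor personnel who do the primary analysis.
- In Section 7.3.1, state that investigators, site staff other than the unblinded pharmacist, participants and site-facing sponsor staff stay blinded until the last Follow-up Week 24 visit.
- Align the Section 10.4.5 sentence with this, or mark it as applying to the interim looks only.
- As a minor tidy-up, use one trigger in Sections 1.1, 5.1.2, 7.3.2 and 10.4.4: the Section 10.4.4 wording, which allows for participants who discontinued, with the Section 7.3.2 data-collection condition. Sections 5.1.2 and 7.3.2 already refer to 10.4.4, so this is consistency only.

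The cost is wording in six sections and a firewall inside the sponsor for up to about 20 weeks. The primary analysis is not delayed.
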